3. STUDY DESIGN

Study design: Single-center, single-blind, pilot randomized controlled trial

Primary outcomes:

- 1) Correlation between physiologic synchrony in patient-provider dyads (GSR or HRV) and improvement in GERD symptom severity.
- 2) Correlation between absolute changes in GSR within subjects over the course of the study visit and subsequent changes in GERD symptom severity.
- 3) Correlation between absolute changes in high frequency HRV within subjects over the course of the study visit and subsequent changes in GERD symptom severity.

Secondary outcomes:

- 1) The difference in the frequency of supportive provider behaviors between the standard and expanded visit groups.
- 2) The difference in the ratings of rapport, engagement, and reciprocity between the standard and expanded visit groups.

Study population:

Men and women age 21-70 with heartburn symptoms 3 or more days per week. We will enroll until we reach 24 completing subjects.

Study location:

The Clinical Research Center (CRC) at Massachusetts General Hospital (MGH), the Benson-Henry Institute (BHI) for Mind Body Medicine, or another MGH location.

Length of subject participation: 2 weeks

Length of study enrollment: 12-14 months

Groups:

- 1) Standard visit (n=8), modeled after an empathic, high quality conventional primary care visit.
- 2) Expanded visit (n=16), modeled after a visit with an integrative medicine provider

Randomization:

The randomization code will be generated by the study statistician as described below (section 4.3). The study will be single-blinded (study providers and the research team will know what the subject is receiving but the subject will not). Randomization will be

Tool Revision History

Version: 11.0

Version Date: 5.8.2020

stratified based on study provider. We anticipate 4 providers each seeing 6 subjects (2 standard visits, 4 expanded visits).

4. SELECTION AND ENROLLMENT OF PARTICIPANTS

4.1 Inclusion Criteria

Research subjects must meet all of the following inclusion criteria to participate in the study:

- Adults ages 21-70 years old (rationale: population of interest, GERD frequency increases with age; adults 70+ are more likely to have complicated disease and/or meet one or more exclusion criteria)
- Heartburn symptoms 3 or more days per week with an average daily symptom severity of 3 or more on a 7 day baseline symptom diary (see section 6.2.2 for description of instrument; rationale: subjects must be symptomatic enough that improvement in symptoms is detectable. This threshold is similar to that seen in my pilot study [61].)
- English language proficiency (rationale: feasibility)
- Willingness to be videotaped and connected to physiologic monitoring devices during the visit (rationale: feasibility/study procedures)

4.2 Exclusion Criteria

Any candidates meeting any of the following exclusion criteria at baseline will be excluded from study participation.

- Diagnosis of Crohn's disease, systemic sclerosis, known active ulcer disease, gastric cancer, or untreated/active Barrett's esophagitis based on subject self-report and/or medical record review (rationale: heartburn symptoms may be due to another, more serious medical illness)
- Heavy alcohol use (> 6 drinks/week for women and > 13 drinks/week for men) based on subject self-report (rationale: can exacerbate heartburn symptoms)
- Pregnant women. Due to the short nature of the study and lack of interventions that will interfere with pregnancy, we will not screen for pregnancy or request female participants to use contraception (rationale: feasibility/physiology of heartburn is different in pregnant women).
- Dementia or significant memory difficulties as determined by the study team and medical record review (rationale: feasibility and human subjects concerns)
- Severe, unstable psychiatric disease based on subject self-report, study team determination, and/or medical record review (rationale: feasibility and human subjects concerns)
- Greater than 15 doses of nonsteroidal anti-inflammatory drugs (NSAIDs) within the prior 30 days (aspirin \leq 325 mg daily permitted) or ongoing NSAID use at a

Tool Revision History

Version: 11.0

Version Date: 5.8.2020

level deemed likely to interfere with the study (rationale: NSAIDS can exacerbate GERD and cause peptic ulcers)

- Failure to complete the baseline symptom diary for at least 6 of 7 days (rationale: feasibility)
- Change in GERD treatment regimen within the last 2 weeks (subjects may use antacids, H2 receptor blockers, and/or proton pump inhibitors as long as they are symptomatic on a stable regimen; rationale: feasibility, need a stable symptom baseline)
- Allergy to adhesives (rationale: feasibility/study procedures)
- Inability to provide informed consent (rationale: human subjects concerns)
- In the opinion of the investigator, unable to comply with the study protocol or has a condition that would likely interfere with the study (rationale: feasibility)

4.3 Study Enrollment Procedures

Patient Recruitment:

Initial recruitment efforts will start with the MGH Internal Medicine Associates (IMA) primary care practice and the Benson-Henry Institute (BHI; clinician referral, flyers in clinic, and posting on the BHI website), but may expand to include a) other MGH primary care practices, b) the MGH gastroenterology clinic, c) Research Study Volunteer Program (RSVP) for Health (an online registry of Partner's affiliated clinical trials), d) the Partners' clinical trials website, e) MGH Broadcast weekly research studies seeking volunteers email, f) clinician referral, g) the Research Opportunities Direct to You (RODY) program, and/or h) flyers posted in clinics and hospital-approved bulletin boards if we are not meeting our recruitment goal of 3-5 subjects/month.

We will begin by identifying potential subjects from the MGH primary care practice-based research network (PBRN) cohort. Potential subjects identified through the PBRN cohort will receive a letter from the study PI informing them of the study and inviting them to participate along with contact information for a study coordinator and a postcard they can mail in if they wish to opt-out and not be contacted. Patients who do not mail back the opt-out card will receive a telephone call from a study team member at least 2 weeks after the letter was mailed. We will seek permission from patients' primary care physicians prior to sending any letters. Letters sent to potential participants that are part of the RODY program will not include an opt-out card, but the study coordinator's number and email with instructions to call or email if they do not wish to be contacted about the study.

Study flyers will be posted in the BHI waiting room to recruit participants. If a patient is interested in learning more about the study, they may request additional information during their appointment or may call the phone number on the flyer. Alternatively, if the investigator sees a patient who may be eligible, she may mention that the BHI is conducting a study for patients with GERD and ask if they would like to receive more information from a study research coordinator. In all cases, prospective subjects will be informed that their decision whether to participate will have no effect on the care they

Tool Revision History

Version: 11.0

Version Date: 5.8.2020

receive at the Institute. The Investigator will address any immediate questions the prospective subject may have and obtain verbal permission to give their contact information to a study staff member who can provide further details.

Patient Screening:

Potential subjects will undergo a telephone prescreen by study staff and have the opportunity to ask questions about the study (see telephone script). Potential subjects will be told that they will not receive specific treatment recommendations for their GERD as part of the study. They will also be informed that the study involves optional blood draws at each visit. If the potential subject receives care at a Partner's Healthcare affiliated institution, their medical record will be reviewed as part of the eligibility assessment. A standardized form (see attached) will be used to ascertain potential eligibility and an electronic screening log will be kept to keep track of reasons for ineligibility. Those who are deemed potentially eligible and are interested in participating will be sent a 7 day baseline symptom diary (by email or via the post office) and scheduled for an intake visit and two week follow-up visit. Potential subjects will be mailed a copy of their medication list (if they are a Partner's patient) and asked to update it or bring a complete list of medications, vitamins, herbs, and supplements that they are taking to the baseline visit. Potential subjects will be called several days after the diary is mailed to ensure that they received it and that the instructions for completing the diary are clear.

Intake Visit and Consent:

Subjects will present to the BHI, the CRC at MGH, or another pre-determined MGH location. The baseline symptom diary will be reviewed by a study team physician (one of the study investigators, not a provider delivering the study visit intervention) and potential subjects will be rescreened. If they are deemed eligible, they will have an opportunity to review the written informed consent document, ask any questions, and will be consented by a study team physician.

To avoid alerting subjects to the fact that we are directly studying the effect of the patient-provider relationship on health outcomes (which could influence study results [66,67]), the study team physician will inform subjects during the consent process that 1) talking about their symptoms with a physician may result in improved autonomic nervous system regulation and improvement in GERD symptoms (to set an expectation for possible symptom improvement and explain why GSR and HRV are being monitored) and 2) we are studying whether physicians mirror patients' physiology as has been suggested by some neuroimaging studies [37,68] (to explain why providers are being similarly monitored). While it is challenging to study patient-provider interactions without subjects' direct knowledge, particularly since both are being monitored in this study, we believe that framing the study in this way is the most sensible way to proceed and the least likely to substantively affect the study's results. As the intervention is minimal risk, we believe it meets the federal criteria for modification of informed consent [69], to allow us to conceal from participants that we are studying the patient-provider interaction.

Subjects will also be informed during the consent process that the healthcare provider who will be asking them about their GERD symptoms has been instructed not to provide any specific GERD treatment advice since they will not have the opportunity to follow-up and

Tool Revision History

Version: 11.0

Version Date: 5.8.2020

because their primary care physician may have a preferred treatment plan for their GERD. We will provide study participants with an informational handout on GERD and possible treatment approaches at the end of the study.

Individuals who sign the informed consent document and elect to participate in the study will be considered enrolled. Only individuals who can provide informed consent will be eligible to participate.

Randomization:

Once enrolled, subjects will be randomized to receive either the standard visit intervention (n=8) or the expanded visit intervention (n=16; section 9.2). They will not know that there are two possible visit choices. This aspect will be revealed to subjects during a debriefing at the follow-up visit. We will stratify by provider and create permuted block sizes of 3 and 6 (2 expanded, 1 standard; 4 expanded, 2 standard) with the intent to enroll 4 providers who will each see 6 subjects. If we can only enroll 3 providers or one provider cannot see 6 subjects then the remaining slots will be divided among the remaining providers.

Provider Recruitment and Screening:

We will approach pre-identified MGH internal medicine physicians and ask whether they are interested in participating in the study as providers. If we cannot identify enough interested physicians internally, we may approach colleagues at other Partners-affiliated institutions and/or send an email describing the study to internists within the MGH Division of General Internal Medicine. We may also present the study at practice meetings or division conferences. Providers must be willing to adhere to the study protocol and not provide specific treatment recommendations (pharmacologic or non-pharmacologic) as this is outside the scope of the study and subjects must remain on a stable regimen during the course of the study. Providers must also be willing to receive a brief training to understand how to deliver the standard and expanded visit interventions.

Provider Consent:

Participating providers will be consented by the study PI. As study providers will deliver both visit interventions, they will not be blinded as to the study's hypotheses or the group to which a given subject is assigned. They will be notified of which intervention they are delivering immediately before walking into the room to conduct the study visit.

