5. STUDY INTERVENTIONS

5.1 Interventions, Administration, and Duration

Standard and Expanded Visit Groups

Subjects will be randomized to receive either a "standard visit" or an "expanded visit" with a study provider. The standard visit is based on a high quality, empathic, conventional primary care encounter. The expanded visit is based on an integrative medicine consultation. Both visits are based on a script of questions and statements to the

Tool Revision History

Version: 11.0

Version Date: 5.8.2020

patient/subject (see Appendix E). The standard visit script includes questions about GERD history, symptoms, prior evaluation and treatments, and past medical history as well as a brief physical exam. The expanded visit script includes the same questions as the standard visit script plus additional questions that inquire about the modalities of their GI symptoms (e.g., nature of the reflux taste, sensation of heartburn pain and/or abdominal fullness, time of day better/worse), details about non-GI symptoms, quality of sleep, the effect of the weather on symptoms, food cravings and aversions, menstrual flow, fears/phobias, and overall temperament. In this way, the expanded visit tries to understand the patient's/subject's constitution in a way that many systems of integrative medicine attempt to do. To reduce the potential for introducing bias by using the words "standard" and "expanded", the visit templates that they study providers will follow will simply refer to the number of questions to be asked on the template (e.g., 6 Question Template).

In our pilot study [61] we did not limit the amount of time spent with the study subject. On average, the standard visit lasted 18 minutes (range 11-32 minutes) and the expanded visit lasted 42 minutes (range 23-74 minutes). The study providers will be instructed to maintain equal empathy in both groups (e.g., kind and friendly manner, maintained eye contact, active listening and repeating back the patient's words, expressions of empathy). Thus, the main differences between the visits will be the length of time spent with the subject and the additional questions that are asked.

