9. STATISTICAL CONSIDERATIONS

9.1 General Design Issues

Design: This is a pilot, proof-of-concept, single-blinded randomized controlled trial in which subjects will be randomized in a 2:1 fashion to receive either an expanded or standard visit intervention. We are including both types of visit interventions and randomizing subjects in this way to maximize our potential to measure a wide range in physiologic concordance within the patient-provider dyads so we can best assess our hypotheses.

Primary hypotheses:

1. Subjects in patient-provider dyads with higher levels of concordance in GSR or HRV (i.e., where patient and provider GSR or HRV change in concert) will demonstrate greater improvement in GERD symptom severity than subjects in patient-provider dyads with lower levels of concordance in these measures.
2. Subjects who experience physiologic changes similar to those elicited by mind-body techniques (i.e., decreased GSR and increased high frequency HRV) over the course of their visit will demonstrate greater improvements in GERD symptom severity than subjects who do not.

Secondary hypothesis:

1. As the expanded visit unfolds, providers will demonstrate significantly more patient-centered, nonverbally supportive behaviors and have higher global impression ratings of rapport, engagement, and reciprocity compared to early in the expanded visit and both early and late in the standard visit.

Primary outcomes:

1. Correlation between physiologic synchrony in patient-provider dyads (GSR or HRV) and subsequent improvement in GERD symptom severity.
2. Correlation between absolute changes in GSR within subjects over the course of the study visit and subsequent changes in GERD symptom severity.

Tool Revision History

Version: 11.0

Version Date: 5.8.2020

3. Correlation between absolute changes in high frequency HRV within subjects over the course of the study visit and subsequent changes in GERD symptom severity.

Secondary outcomes:

1. The difference in the frequency of supportive provider behaviors between the standard and expanded visit groups.
2. The difference in the ratings of rapport, engagement, and reciprocity between the standard and expanded visit groups.

Validity and reliability of outcome measures:

1. Assessment of physiologic concordance has been described by a number of groups and we will be using similar methodology [42,78].

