9.5.2 Secondary Outcomes

1. The difference in the frequency of supportive provider behaviors between the standard and expanded visit groups.
2. The difference in the ratings of rapport, engagement, and reciprocity between the standard and expanded visit groups.

Tool Revision History

Version: 11.0

Version Date: 5.8.2020

The number of nonverbally supportive behaviors and impression ratings of the patient-provider interaction will come from coding of video recordings of the patient provider interactions (study visit 1).

We hypothesize that the frequency/intensity of supportive provider behaviors increases as the expanded visit unfolds, compared to the standard visit, as rapport, engagement, and reciprocity between patient and provider increase. Briefly, thin slices (1.5 minutes) of video occurring near the beginning and end of the standard visit (and also a time point in the middle of the expanded visit roughly equivalent to the end of the standard visit) will be analyzed by trained coders, blinded to the study hypotheses, for the presence of 1) micro-level nonverbally supportive behaviors (e.g., friendly voice quality, leaning forward, open body posture, eye contact, nod, smile, and gestures) as well as 2) macro-level impression ratings of the interaction (e.g., rapport, engagement, reciprocity).

The PI will meet weekly with the coders to review findings and resolve areas of disagreement until greater than 80% concordance is achieved between coders. Frequency of supportive behaviors and ratings of interactions will be compared using generalized linear mixed models as appropriate for each outcome (e.g., occurrence of binary events, counts of discrete events, ordinal ratings of rapport or engagement). The models will include terms for time-point, visit group assignment, and their interaction.

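### Delivering both visits requires providers to know the visit type, not the directional hypothesis about their own behaviour, and knowing it could bias the secondary comparison

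*Combined protocol and SAP*

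**What the plan says.** On provider consent, section 4.3 reasons that since providers deliver both interventions, they are left unblinded to the study's "hypotheses or the group to which a given subject is assigned". On timing it adds: "They will be notified of which intervention they are delivering immediately before walking into the room to conduct the study visit".

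The first secondary outcome in section 9.1 is about those same providers: "The difference in the frequency of supportive provider behaviors between the standard and expanded visit groups". The second compares ratings of rapport, engagement and reciprocity. The secondary hypothesis in 9.1 has a direction. As the expanded visit unfolds, "providers will demonstrate significantly more patient-centered, nonverbally supportive behaviors", together with higher global ratings, than early in that visit and than early or late in the standard visit.

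Under section 9.5.2 the behaviours are coded from short video slices. The examples given are "friendly voice quality, leaning forward, open body posture, eye contact, nod, smile, and gestures". The slices "will be analyzed by trained coders, blinded to the study hypotheses", and the mixed models contain time-point, visit group and their interaction.

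Section 5.1 labels the templates by number of questions so that providers do not read the words standard and expanded. It also says: "The study providers will be instructed to maintain equal empathy in both groups". The PI reviews the videos, gives providers feedback, and interviews each provider as he or she finishes.

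**The concern.** The reason given in section 4.3 covers half of its conclusion. A provider cannot run a visit without knowing which template to use, so allocation cannot be hidden. Running it calls for the template, the script and the orientation in 5.1. None of these needs a statement of what the investigators expect the provider's behaviour to do.

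In most trials an intervention provider's knowledge of the hypothesis matters indirectly. Here the provider's conduct is the endpoint, and much of what is coded can be varied at will. The plan already accepts the principle elsewhere. It conceals the interaction focus from subjects because knowing it may change their responses (4.3, 5.2), blinds the coders to the hypotheses (9.5.2), and neutralises the template names (5.1). A neutral name protects less if the reader knows what is predicted for the longer template.

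At stake is the reading of the secondary aim. Part of an observed difference, or of an observed lack of one, could come from provider expectation rather than visit format.

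**Working it through.** The documents state no precision or power figure for the behavioural outcomes. The sample-size statement in 9.2 concerns the primary correlation only, so there is nothing to reproduce. The check is of the text and the model.

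**1. What each safeguard protects**

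| Safeguard | Section | Protects | Provider's conduct in the room? |
|---|---|---|---|
| Coders blinded to hypotheses | 9.5.2 | Coding | No |
| Blinded analysis | 6.2.3 | Analysis | No |
| Notification just before the visit | 4.3, 5.2, 6.2.3 | Staff dealings with subjects, recruitment, consent | No: visit type is known throughout the visit |
| Neutral template names | 5.1 | Labelling | Partly, if the prediction is unknown |
| Stratification by provider | 4.3, 9.2 | Differences between providers | No: each provider is to deliver 4 expanded and 2 standard visits, so expectation acts within provider |
| Equal-empathy instruction | 5.1 | Conduct | Yes, but it pushes towards no difference |

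**2. What the planned model would do with an expectation effect**

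Let e(g,t) be the shift in coded behaviour due only to expectation, on the model's scale, for group g (E expanded, S standard) at time t (early, late).

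- Group contrast averaged over early and late: bias = [e(E,early) + e(E,late)]/2 − [e(S,early) + e(S,late)]/2.
- Group-by-time interaction: bias = [e(E,late) − e(E,early)] − [e(S,late) − e(S,early)].

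Case A, a constant shift u throughout the expanded visit and none in the standard visit: group bias = (u + u)/2 − 0 = u; interaction bias = (u − u) − 0 = 0.

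Case B, a shift only late in the expanded visit, of size u: group bias = (0 + u)/2 − 0 = u/2; interaction bias = (u − 0) − 0 = u.

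A constant shift therefore cancels in the interaction but not in the group difference, which is what 9.1 names as the outcome. The hypothesis in 9.1 makes three comparisons with late expanded behaviour. In case A the one with early expanded is unbiased, and those with early and late standard are each biased by u. In case B all three are biased by u.

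**3. Direction**

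Expectation alone would make u positive. The equal-empathy instruction works the other way. Its examples (manner, eye contact, active listening, expressed empathy) overlap two of the seven coded examples in 9.5.2, friendly voice and eye contact. The other five (leaning forward, posture, nod, smile, gestures) are not named. The sign of the net effect is not fixed by the text.

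**4. Size**

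No document gives a value for u or a standard deviation for coded behaviour. A rejection rate computed from an assumed u would only restate the assumption, and a two-sample test on one value per visit is not the planned mixed model. No figure is offered.

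**The case against.** The strongest case on the other side has five parts.

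- **The plan already counters the bias.** Providers are told to show equal empathy. This stands as a reason not to assert a direction. It does not remove the problem: providers unblinded to a predicted difference are also told to show none.
- **The time-course design protects the hypothesis.** It protects the interaction, and the early-versus-late comparison within the expanded visit, against a constant shift. It does not protect the group difference, or any contrast if expectation builds during the visit.
- **Masking may be nominal.** Providers train in both visits, wear sensors, are filmed, receive feedback, and can see that one template is longer. They may guess. This stands: withholding the hypothesis reduces the bias and may not remove it.
- **Concealment from providers is a new ethical step.** Sections 4.3 and 5.2 justify altered consent for subjects, not for providers, who give their own written consent. This stands, and it is a cost of the fix.
- **The stakes are low.** Provider non-blinding is openly declared, and this is a secondary aim in a 24-dyad pilot. This stands, and it sets the grade.

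A reader might also infer that providers are told the directional prediction. Section 4.3 says only that they are not blinded to the hypotheses. The provider consent form and recruitment materials are not in the text reviewed, so what providers actually learn cannot be checked here.

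**Conclusion.** The point holds as a cheap improvement. The reason in section 4.3 supports unblinding to visit type and not to the hypotheses. Knowledge of the directional prediction could bias the comparison of provider behaviours and interaction ratings between visit types. It could also bias the group-by-time pattern if expectation acts more as the visit proceeds. The direction is uncertain and the size cannot be estimated from the documents.

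This rests on two assumptions: that being unblinded means providers may come to know the behavioural prediction, and that coded behaviour can respond to that knowledge.

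Two stronger readings are tempting. One is that a difference in supportive behaviour would show only that providers knew what was expected. The other is that the secondary aim cannot separate format from expectation at all. The documents support neither: the equal-empathy instruction opposes the predicted difference, and the interaction is unaffected by a constant shift.

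**What to change.** 1. In section 4.3, state that providers are not blinded to visit type, and remove the statement that they are not blinded to the hypotheses.
2. At provider consent and orientation, describe the two templates, the physiologic monitoring and the video recording, without the directional behavioural hypothesis.
3. Keep that hypothesis out of the PI's video feedback (5.1, 9.4), and limit the feedback to fidelity to the script and instructions.
4. Disclose it after provider visits are complete. The exit interview in 5.1 is a natural place, but it takes place as each provider finishes. Either hold disclosure until the last provider is done or ask early finishers not to inform the others.
5. If providers have already been informed, state this as a limitation, and interpret the secondary result as the effect of visit type delivered by hypothesis-aware providers.

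The cost is new wording for provider consent and orientation, an IRB amendment with its own justification for partial disclosure to about four provider participants, and the acceptance that some may guess. Sample size, data collection and the planned models are unchanged.
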